### **Creatinine method evaluation**

Method comparison will be performed by comparing creatinine results obtained by enzymatic assay on the Roche platform with results obtained by LC-MS/MS. A minimum of 50 patient samples will be analysed, as well as EQA samples. Within and between batch precision will be performed by loading Mitra® devices with IQC sample. 3 levels of IQC will be run a minimum of 5 times within the same analytical run and between analytical runs, on different days. Precision studies will be used to determine the LLOQ. Low patient pools will be prepared to give appropriate concentrations. Samples will be analysed 10 times within the same analytical run and 10 times between runs.

Linearity will be determined by performing dilutions of the creatinine standard material to prepare an extended standard curve. To assess recovery, blank samples will undergo sample preparation steps and will be spiked with the 3 different levels of creatinine QC. Carryover will be assessed by analysing an alternating high creatinine concentration sample with repeated analysis of a low creatinine or blank sample.

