**Background (*Literature review*):**

Tacrolimus is an immunosuppressant which acts by inhibition of calcineurin. It's typically used as a first line drug to prevent allograft rejection in renal transplant patients (1). With pharmacokinetic variability between patients and a narrow therapeutic range, therapeutic drug monitoring (TDM) is essential to support graft survival. Low levels of tacrolimus risk organ rejection, whilst toxic levels risk nephrotoxicity and other adverse effects including neurotoxicity, electrolyte disturbances and hyperglycaemia (2). Clinical guidelines suggest target tacrolimus ranges, but levels are determined by renal clinicians and are patient specific, depending on individual circumstances, as well as the time since transplantation (3).

Renal transplant patients require lifelong monitoring of immunosuppressant levels and renal function to assess graft kidney stability. Renal function is monitored by measuring serum creatinine and urine protein excretion, levels of which determine the need to perform a biopsy if graft dysfunction is suspected (3). Creatinine is the product of creatine phosphate catabolism in muscle. Its endogenous production at a constant rate and clearance by glomerular filtration makes it a useful marker of graft function, with increasing levels indicating a reduced glomerular filtration rate and thus some element of renal disease (4). Creatinine is measured enzymatically on the Roche platform, as part of a urea and electrolyte panel.

The Renal department is currently managing just under 1000 patients with a functioning kidney transplant, with this number increasing annually. There are 80-100 transplants per year and a current waitlist of just under 300 patients. Following successful transplantation, every patient requires lifelong monitoring of transplant function. This is not only a long-term commitment for these patients, but also the renal department in providing the aftercare. Current practice for post-transplant monitoring involves regular venepuncture to collect a venous blood sample for tacrolimus measurement and a 'dialysis profile' (urea and electrolytes, bicarbonate, CRP). Clinical guidelines recommend monitoring tacrolimus levels by trough sample 3 times a week initially. Frequency decreases over time to every 4-6 weeks at 6-12 months and then every 3-6 months at 12 months post-transplant, unless adjustments are made to the dosage which warrants more frequent

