#### **Creatinine method evaluation**

Precision: The following statistics will be calculated for within and between batch precision: mean, SD and %CV. A CV less than 20% will be deemed acceptable.

Accuracy: All samples will be analysed in duplicate and the results averaged. Passing-Bablok regression and Pearson correlation coefficient will be used to compare and assess correlation of the results obtained from each method. Bland-Altman analysis will assess agreement and determine presence of any bias between the results obtained from the different methods. 95% confidence intervals will be calculated. Statistical analysis will be performed using the Analyse-It add-in for Microsoft Excel.

Linearity: The diluted creatinine standards will be analysed in duplicate and plotted against the concentration to give the  $r^2$  value. Means should be within 15% of each other to confirm linearity.

LLOQ: Mean, SD and %CV will be calculated. LLOQ will be defined as the level with a between batch precision of <15%.

Recovery: Each level of QC will be run in triplicate and the average calculated, with the recovery being expressed as a percentage with an acceptability of 100±20%.

Carryover: The % carryover from high to low concentrations will be determined. Differences of ±15% will be deemed acceptable.

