#### **Sample collection comparison**

All samples will be analysed in duplicate and the results averaged. Passing-Bablok regression and Pearson correlation coefficient will be used to compare and assess correlation of the results of venous and capillary samples. Bland-Altman analysis will assess agreement and determine presence of any bias between the results obtained from venous and capillary sample collection. 95% confidence intervals will be calculated. Statistical analysis will be performed using the Analyse-It add-in for Microsoft Excel.

Stability: Samples will be analysed in duplicate and the results averaged. Means of each group will be

calculated and compared to baseline. Differences of  $\pm 15\%$  will be deemed acceptable.

**Effect of haematocrit concentration:** The 4 samples will be analysed in duplicate and the results averaged. Differences of 15% will be deemed acceptable and this would confirm samples collected using Mitra® devices are unaffected by differing haematocrit concentrations.

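### As worded, the creatinine recovery test spikes already prepared blanks, loads no QC on the Mitra tip and names no comparator, so its 100±20% limit need not reflect extraction loss

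*Protocol*

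**What the plan says.** In the protocol's Methodology, under Creatinine method evaluation, the recovery procedure is a single sentence: "blank samples will undergo sample preparation steps and will be spiked with the 3 different levels of creatinine QC". Preparation is named first and the spike second. No loading of the sampling device is mentioned, and no second set of samples.

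Earlier in the same section the precision work is described differently: "Within and between batch precision will be performed by loading Mitra® devices with IQC sample". It uses three IQC levels, each run at least five times. Device loading is therefore stated for precision but not for recovery.

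Under Data Analysis, Creatinine method evaluation, the recovery entry gives the replication as "Each level of QC will be run in triplicate and the average calculated". The acceptance limit, in per cent, is set out there as "with the recovery being expressed as a percentage with an acceptability of 100±20". Neither numerator nor denominator is defined. For precision, the rule is "A CV less than 20% will be deemed acceptable".

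The Sample collection comparison section plans a Bland-Altman analysis of paired patient samples to "determine presence of any bias between the results obtained from venous and capillary sample collection". Under Deriving a new reference range, a bias that matters clinically is first confirmed with more patient data and is then used to set a new range for patients monitored with the device.

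**The concern.** Extraction from the tip is a step that a serum method does not have, and the reference list identifies the published method on which this assay is to be based as a serum creatinine assay. A recovery experiment is where one would expect to learn how much creatinine the tip gives up. Creatinine added to a blank after preparation has never been on the tip and has not passed through extraction, so its measured percentage carries no information about release.

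If the test is run that way, the assay can be declared acceptable on recovery while a substantial constant loss is present. That loss could then appear as a difference between capillary and venous results, be read as a property of the sampling route, and be built into a new reference range when it should have been corrected in the assay.

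**Working it through.** **Inputs.** From the protocol: acceptance window 80% to 120%; three QC levels; three replicates per level for recovery; precision limit CV below 20%. Not in the protocol, so assumed: fraction released from the tip, E = 20% to 100%; matrix effect, M = 0.9 to 1.1, where 1 means none. The plan states only an acceptance limit here, so there is no derived figure to reproduce.

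**Three readings of the recovery text.**

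- A. Blank spiked after preparation, divided by nominal: 100 × M.
- B. QC loaded before preparation, divided by nominal: 100 × M × E.
- C. QC loaded and extracted, divided by blank spiked after preparation: 100 × (M × E) / M = 100 × E, if M is the same in both arms.

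**Results (%), for M = 0.9 / 1.0 / 1.1.** F marks a result outside 80% to 120%.

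| E | A | B | C |
|---|---|---|---|
| 100% | 90 / 100 / 110 | 90 / 100 / 110 | 100 |
| 90% | 90 / 100 / 110 | 81 / 90 / 99 | 90 |
| 80% | 90 / 100 / 110 | 72 F / 80 / 88 | 80 |
| 79% | 90 / 100 / 110 | 71.1 F / 79 F / 86.9 | 79 F |
| 50% | 90 / 100 / 110 | 45 F / 50 F / 55 F | 50 F |
| 20% | 90 / 100 / 110 | 18 F / 20 F / 22 F | 20 F |

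Under A the rule passes at every E. Under B it fails once M × E falls below 0.80, that is at E below 0.80/0.9 = 89% when M = 0.9 and below 0.80/1.1 = 73% when M = 1.1. Under C it fails below E = 80% whatever M is.

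**Do the other acceptance rules cover the gap?**

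- Precision: a constant proportional loss multiplies SD and mean alike, so CV = (E × SD)/(E × mean) is unchanged.
- Stability: results are compared with baseline, so a constant loss cancels.
- Haematocrit: judged on differences of 15%, so a loss common to all four levels cancels.
- Linearity and EQA: neither is said to involve loaded tips.
- Paired comparison: it could show a net loss as bias, but it sets capillary whole blood against serum, so it cannot assign that bias to extraction.

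**Blank handling in a ratio of type C.** Take a nominal level of 150 µmol/L and full release (both assumed). If the spiked reference arm carries background creatinine of 0, 30 or 60 µmol/L (assumed) and nothing is subtracted, the ratio is 150/150 = 100%, 150/180 = 83% or 150/210 = 71%. Subtracting 60 from both arms, when only the reference arm contains it, gives (150 − 60)/(210 − 60) = 60%. Subtracting it only from the arm that contains it gives 150/(210 − 60) = 100%.

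**The case against.** The strongest reply is that reading A is only one way to take a loosely written sentence. The two steps are joined without a word that fixes their order, and the Data Analysis text speaks of running QC, not of running spiked blanks. A blank spiked after preparation is a proper 100% reference, and the protocol already plans tip-loaded IQC at three levels. Reading C may be what the laboratory intends, and under it the rule detects any loss above 20%. This stands: a reader might infer that the plan certainly cannot detect extraction loss, and the text does not support that. It is equally true that the protocol never states the comparison that would make the rule work.

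Second, a large loss might be noticed elsewhere. The precision work calculates the mean of tip-loaded IQC, and a shortfall would be visible there if target values exist and calibrators are not on tips; the protocol states neither, and sets no limit on that mean. If calibrators are prepared on tips, a constant loss would largely cancel in the reported results. The paired comparison could also reveal a net bias. These points reduce the consequence but do not repair the test.

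Third, a reader might infer from "Its endogenous production at a constant rate and clearance by glomerular filtration makes it a useful marker of graft function" that the blanks contain creatinine and inflate recovery. That sentence in the Background concerns production in patients. The protocol gives no creatinine content for its blank, and its carryover test names a blank as an alternative to a sample low in creatinine. This supports running an unspiked blank as a precaution, and no more.

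Fourth, one could say that bench detail belongs in departmental procedures. But the protocol itself describes the procedure and attaches a pass/fail limit to it, so the limit should be tied to a defined quantity.

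**Conclusion.** The point holds in a limited form. The creatinine recovery test is ambiguously specified. Taken in its written order against the nominal amount, it measures matrix effect and not release from the tip, and it would pass at any extraction loss. Two laboratories following the text could reach opposite conclusions: at an assumed 50% release with no matrix effect, one reports 100% and passes while the other reports 50% and fails. The limit can detect loss only if QC that has been on the tip and through extraction forms the numerator, which the protocol does not say. No other acceptance rule isolates a constant loss.

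The size rests on assumed values of E and M, and reading C also assumes an equal matrix effect in both arms. The documents give no evidence that release is actually poor. The matter should be settled before the method evaluation is run, because the later comparison can show a bias without explaining it.

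**What to change.** In both Creatinine method evaluation sections (Methodology and Data Analysis), define recovery at each of the three levels as:

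- numerator: mean result for IQC loaded on the Mitra tip and taken through extraction;
- denominator: mean result for prepared blank-tip extract spiked afterwards to the same nominal amount.

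Apply 100±20% to that ratio. Run an unspiked prepared blank in the same run, and subtract its signal only from an arm that contains that blank. State also whether calibrators are prepared on tips, so that the effect of a constant loss on reported results can be judged.

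The cost is small. Tip-loaded IQC at three levels, at least five times each, is already planned for precision, and the spiked blanks are already planned for recovery. What is added is wording and one unspiked blank per run.

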### **Sample collection comparison**

To compare results collected by venepuncture and results collected by VAMS® sampling, a minimum of 50 paired patient samples will be analysed for tacrolimus and creatinine by LC/MS-MS. 20 EQA samples from the NEQAS immunosuppressant scheme will be analysed for tacrolimus and 20 EQA samples from the NEQAS clinical chemistry scheme will be analysed for creatinine by LC-MS/MS. To compare creatinine methods (enzymatic and LC-MS/MS), creatinine samples will also be analysed using an enzymatic assay on the Roche platform.

To test the stability of whole blood collected by VAMS®, 5 samples will be stored at varying temperatures for 7, 14 and 21 days. The samples will be stored at -20°C, 4°C, room temperature and

37°C. This will test the effect of temperature extremes which may occur due to postal delivery of the Mitra® devices. The stability of post extraction samples will also be tested by storing the 96 well plate at 4°C post analysis and re-assaying at 24 and 48 hours post extraction. To investigate the effect of different haematocrit concentrations, blood cells and plasma will be mixed 20:80, 40:60, 60:40 and 80:20 to obtain 4 different haematocrit levels (20%, 40%, 60% and 80%).

#### **Deriving a new reference range**

If the LC-MS/MS tacrolimus and/or creatinine method shows a clinically significant bias compared to current methods, this will be confirmed by obtaining further patient comparison data. If confirmed, the reference range will need to be reviewed and amended accordingly. Any bias identified by Bland-Altman analysis will be used to derive a new reference range for patients being monitoring using blood collected using the Mitra® devices.

#### **Data Analysis**

Statistical analysis will be performed based on CSLI recommendations and departmental protocols.

Study population characteristics (including patient age, tacrolimus dose, time since transplantation, haematocrit) will be expressed as median (range).

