#### **Rationale and Significance of Study:**

The main advantage of this collection method is that it allows the remote collection of a blood sample. This reduces patient attendance at blood clinics and resultant strains on phlebotomy staff and clinics, eliminates administration requirements for transplant nurses and saves both the patient and the NHS time and money. Of most importance is the great flexibility and convenience this collection device offers, as patients can collect samples at anytime and anywhere, providing greater freedom compared to current procedures.

Patient adherence to immunosuppressants is a key factor in potential graft rejection, with lack of immunosuppression leading to graft loss, even years after transplantation (12). Due to the increased flexibility offered by the Mitra® device, it is anticipated that this collection method will improve patient compliance with TDM. Better timed sample collection is also expected (ie. a 'true' trough sample) as patients are not subject to blood clinic operating hours. Consequently, potentially more frequent and better-timed sample collections will be more clinically useful.

Importantly for patient management, is the ability to calculate AUC (area under the curve). This is not currently possible with current protocols as regular samples would be required which inconveniences the patient. AUC targeted therapeutic monitoring of tacrolimus may be more clinically informative than current pre-dose tacrolimus measurements and be a better indicator of immunosuppressant efficacy (13).

It is also worth noting the current issues encountered with venepuncture for venous blood collection. Increased patient anxiety occurs because of needle phobia (although uncommon) and if the patient is difficult to bleed. The latter of which can result in lengthy appointments whilst the required samples are obtained. In comparison, capillary blood sampling is minimally invasive, and a much smaller volume of blood is required (particularly useful for the elderly). However, a well-known issue associated with capillary blood is the volumetric haematocrit bias and poor blood spot quality, resulting in non-homogenous samples and inaccurate results (14). This issue is alleviated using Mitra® devices because a defined blood volume is collected.

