**Definition of the end of study:**

The trial will end once enough samples have been collected to cover the required range of tacrolimus and creatinine concentrations for the assay. This will be a minimum of 50 samples. Only a single sample is required from each patient and there will be no follow up of the same patient. Patients will continue to be monitored post-transplant and have blood samples taken throughout the time of the study as part of the routine care, but they will not be included in the study.

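### Four laboratory mixtures are allowed to settle haematocrit independence, while patient haematocrit is only tabulated and never related to the tacrolimus capillary-venous difference in the real pairs

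*Protocol*

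**What the plan says.** The Protocol's rationale section names the problem: "a well-known issue associated with capillary blood is the volumetric haematocrit bias and poor blood spot quality". It then says that the device's fixed collection volume alleviates it.

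Two strands of the plan bear on this.

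- **Real pairs.** Under Methodology, Sample collection comparison, "a minimum of 50 paired patient samples will be analysed for tacrolimus and creatinine by LC/MS-MS". The end-of-study definition adds that "Only a single sample is required from each patient and there will be no follow up of the same patient". The analysis of the pairs, in the Data Analysis subsection of the same name, is: "Passing-Bablok regression and Pearson correlation coefficient will be used to compare and assess correlation of the results of venous and capillary samples" and "Bland-Altman analysis will assess agreement and determine presence of any bias between the results obtained from venous and capillary sample collection". Haematocrit has no part in it. Patient haematocrit appears only in the opening of Data Analysis: "Study population characteristics (including patient age, tacrolimus dose, time since transplantation, haematocrit) will be expressed as median (range").
- **Laboratory mixtures.** Under Methodology, "blood cells and plasma will be mixed 20:80, 40:60, 60:40 and 80:20 to obtain 4 different haematocrit levels (20%, 40%, 60% and 80"%). Data Analysis has these four samples run in duplicate and sets the rule: "Differences of 15% will be deemed acceptable and this would confirm samples collected using Mitra" devices do not depend on haematocrit. No reference sample is named for the 15%.

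The section on deriving a new reference range would use whatever bias the Bland-Altman analysis finds.

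**The concern.** The protocol identifies haematocrit as a recognised source of error in capillary blood and lists it as a patient variable, but never sets it against the differences it might explain. For tacrolimus both members of a pair are whole blood from the same patient (Methodology, Sample analysis), so the paired difference against that patient's haematocrit is the most direct evidence the study could give.

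An error that changes sign across the haematocrit range can average to nothing. The overall Bland-Altman bias would then look acceptable, and the dependence would show only as wider limits of agreement with no identified cause. A reference range shifted by one overall bias would not correct it: patients at the low end would be misread one way and those at the high end the other.

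The protocol does more than leave an analysis unmentioned. It fixes the rule by which independence is declared, and that rule draws on the four mixtures alone.

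**Working it through.** The protocol gives no variance, power or effect size behind its minimum of 50, so there is no stated figure to reproduce.

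**Inputs from the Protocol:** at least 50 pairs, one per patient; mixtures at 20, 40, 60 and 80%, in duplicate; limit 15%.

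**Assumptions:** the 40% mixture is the reference; any effect is linear; patient haematocrit SD is 5 points; SD of the percent difference is 8 to 15%; assay CV in the mixture experiment is 5 to 10%.

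**1. What the 15% rule lets through.** For slope b (% per point), the shift against the 40% mixture is b × (haematocrit − 40).

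- b = 1: −20% at 20, +20% at 60, +40% at 80. All exceed 15%, so the mixtures would probably catch it.
- Largest slope within the limit, set by the 80% mixture: b = 15/(80 − 40) = 0.375.
- Between patients at 25% and 45%: 0.375 × 20 = 7.5 percentage points.
- If the 20% mixture were the reference instead: b = 15/(80 − 20) = 0.25, and 0.25 × 20 = 5 percentage points.

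**2. How informative a pass or fail is.** Simulated normal error on duplicate means, with all three comparisons against the 40% mixture required to fall within 15%:

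| Assumed CV | True slope (% per point) | Chance of passing |
|---|---|---|
| 5% | 0 | 99% |
| 5% | 0.25 | 79% |
| 5% | 0.375 | 45% |
| 10% | 0 | 70% |
| 10% | 0.25 | 47% |
| 10% | 0.375 | 29% |

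A moderate slope often passes. At CV 10%, no effect at all fails about 30% of the time.

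**3. What a regression on 50 pairs would give.** SE(slope) = SD_diff / (SD_hct × √(n − 1)), with √49 = 7 and t(0.975, 48) = 2.01.

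| SD of difference | SE (% per point) | 95% half-width, 10 points | 95% half-width, 20 points |
|---|---|---|---|
| 8% | 8/35 = 0.229 | ±4.6 | ±9.2 |
| 12% | 12/35 = 0.343 | ±6.9 | ±13.8 |
| 15% | 15/35 = 0.429 | ±8.6 | ±17.2 |

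**4. Power.** The correlation detectable with 80% power at two-sided 5% is tanh((1.960 + 0.842)/√47) = 0.39. As a slope, 2.80 × SE gives 0.64% per point (SD 8%) to 1.20% per point (SD 15%). Both exceed 0.375, so the pairs alone would not reliably detect a slope that just meets the mixture limit.

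**The case against.** The strongest objection is that the plan already tests haematocrit over 60 points, far wider than patients would span, with a numerical limit. A reader might infer that a large error could pass unnoticed because the pairs are not regressed. The documents do not support that for a linear effect that also appears in the mixtures: 1% per point fails in step 1. A slope of 0.25% per point amounts to 10% between the 40% and 80% mixtures, so passing it is consistent with the plan's own tolerance. This stands, and it limits the size of the point.

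Precision is a second fair objection. Over 20 haematocrit points the half-width reaches ±17.2, beyond the 15% limit. This also stands: the regression is supportive and is not a test that could establish independence.

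Third, a reader might infer that the data are in hand for every patient. The protocol lists haematocrit only as a characteristic to summarise. It does not say that it is measured at the paired draw, and the routine tests named in the background include no blood count.

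Fourth, a covariate analysis of this kind is often left to an analysis plan, which is not shown here, and Data Analysis defers to laboratory-standards recommendations and departmental protocols. That would answer a complaint of mere omission. It does not answer the sentence that lets the mixtures confirm independence, because the protocol itself fixes that.

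**Conclusion.** The point holds in a limited form. The conclusion drawn from four mixtures in duplicate goes further than they can support. They do not reproduce finger-prick collection, their reference is not named, and linear slopes up to about 0.375% per point (7.5 percentage points between 25% and 45%) fit within the limit if the 40% mixture is the reference. The real tacrolimus pairs could supply direct evidence, and the protocol plans no such use of them.

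Two stronger readings are not supported. The main venous-capillary comparison is not invalidated by the missing haematocrit term. Nor does the same regression carry over to creatinine: its venous sample is serum, so a slope there would mix matrix and device effects.

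The precision figures rest on assumed SDs, since the protocol gives none. On them, 50 pairs can reveal a large effect and put an interval on it, but cannot rule out a small one.

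**What to change.** In Data Analysis, Sample collection comparison:

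- Add a supportive analysis for tacrolimus: plot and regress the percent difference (Mitra minus venous) on patient haematocrit from the same draw or the nearest available one. Report the slope with its 95% CI, and the predicted difference at the lowest and highest observed haematocrit, set against the 15% limit.
- Name the reference for the 15% in the mixture experiment.
- Reword the conclusion so that a pass in the mixtures counts as supporting evidence, read together with the regression, and does not by itself establish independence.

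The cost is small: one extra analysis, no additional capillary samples, and the need for a haematocrit value close to the paired draw. The protocol should say how that value is obtained.
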